4.1.4. Last Available Value

The last available value is the last nonmissing measurement obtained after starting the study treatment.

4.1.5. Handling of Missing and Incomplete Data

Missing observations will be handled for specific endpoints as detailed in the sections addressing each analysis.

4.2. Variable Definitions

4.2.1. Body Mass Index

Body mass index will be calculated as follows:

$$\text{BMI (kg/m}^2\text{)} = [\text{weight (kg)}] / [\text{height (m)}]^2$$

4.2.2. Body Surface Area

Body surface area will be calculated based on the Mosteller ([1987](#)) formula as follows:

$$\text{BSA (m}^2\text{)} = \{[\text{weight (kg)} \times \text{height (cm)}] / 3600\}^{1/2}.$$

Sites will also record the BSA calculated per institutional standards.

4.2.3. Prior and Concomitant Medication

Prior medication is defined as any nonstudy medication started before the first dose of itacitinib or corticosteroids for participants on corticosteroids only in the Part 1 expansion.

Concomitant medication is defined as any nonstudy medication that is started accordingly:

- Before the date of first administration of itacitinib or corticosteroids only and is ongoing throughout the study or ends on/after the date of first itacitinib or corticosteroid administration.
- On/after the date of first administration of itacitinib or corticosteroids only and is ongoing or ends during the course of itacitinib or corticosteroid treatment.

A prior medication could also be classified as "both prior and concomitant medication" if the end date is on or after the first dose of itacitinib or corticosteroids only. Since corticosteroids are part of the study medication, they will not appear in the list of prior and concomitant medications unless prescribed for an indication other than GVHD. In the listing, it will be indicated whether a medication is prior only, concomitant only, or both prior and concomitant.

For the purposes of analysis, all medications will be considered concomitant medications unless the medications can unequivocally be defined as not concomitant.

5. STATISTICAL METHODOLOGY

5.1. General Methodology

Unless otherwise noted, SAS® software (SAS Institute Inc, Cary, NC; v9.4 or later) will be used for the generation of all tables, graphs, and statistical analyses. Descriptive summaries for continuous variables will include, but not be limited to, the number of observations, mean, standard deviation, median, minimum, and maximum. Descriptive summaries for categorical variables will include the number and percentage of participants in each category.

5.2. Treatment Groups

5.2.1. Part 1

A total of 20 participants with moderate or severe cGVHD will be randomized 1:1 to itacitinib 200 mg QD plus corticosteroids or itacitinib 300 mg QD plus corticosteroids.

5.2.2. Part 1 Expansion

A total of up to 140 participants (35 per treatment group) with moderate or severe cGVHD will be randomized 1:1 to 1 of 4 treatment groups: itacitinib 300 mg QD plus corticosteroids (Treatment Group A), itacitinib 400 mg QD plus corticosteroids (Treatment Group B), itacitinib 300 mg BID plus corticosteroids (Treatment Group C), or corticosteroids monotherapy (Treatment Group D).

5.3. Analysis Populations

The populations that will be included in study-related analyses are described in [Table 4](#).

Table 4: Populations for Analysis

| Population | Description |
|---------------|---|
| ITT | All randomized participants |
| Safety | All enrolled/randomized participants who received at least 1 dose of study drug and/or reference therapy. Treatment groups for this population will be determined according to the actual treatment the participant received regardless of assigned study drug treatment. |
| Safety run-in | All participants enrolled in the safety run-in portion of the study who received at least 1 dose of study drug and/or reference therapy. Treatment groups for this population will be determined according to the treatment assignment on Day 1 regardless of the actual study drug the participant might take during their continued participation in the study. |
| PK evaluable | All participants who received at least 1 dose of study drug and/or reference therapy and provided at least 1 postdose plasma sample (1 PK measurement). The study pharmacokineticist will review data listings of study drug administration and sample records to identify participants to be excluded from analyses of PK data. |

6. BASELINE, EXPOSURE, AND DISPOSITION VARIABLES AND ANALYSES

[Appendix A](#) provides a list of planned tables, figures, and listings.

6.1. Baseline Demographics, Physical Characteristics, and Disease History

Demographic and baseline characteristics, disease history, and prior therapy will be summarized for the safety run-in and Part 1 expansion populations and listed.

6.1.1. Demographics and Baseline Characteristics

The following demographic and baseline characteristics will be summarized for the safety run-in population and Part 1 expansion: age, sex, race, ethnicity, weight (by sex), height, BMI, BSA, and Karnofsky performance status.

6.1.2. Disease History for Chronic Graft-Versus-Host Disease

Baseline cGVHD staging and grading, time since diagnosis of cGVHD, organs involved, aGVHD (yes/no) and grade, conditioning and prophylaxis therapy, donor type, and other details related to the disease under study and transplant will be summarized at baseline. Day 1 assessment will be used to determine baseline organ involvement.

Time since cGVHD diagnosis will be calculated as:

$$\text{Time since diagnosis (years)} = (\text{Day 1 date} - \text{date of diagnosis} + 1) / 365.25.$$

6.1.3. Medical History

For participants in the safety run-in population and participants in the Part 1 expansion, medical history will be summarized by assigned treatment group. This summation will include the number and percentage of participants for each body system/organ class as documented on the eCRF.

6.1.4. Primary Hematologic Disease and Transplant Characteristics

Summary will include disease-targeted medical and treatment history such as participant's primary hematologic disease, including diagnosis, prior therapy, disease stage at the time of transplantation, disease risk index, and details regarding allogeneic hematopoietic stem cell transplantation; prior and current GVHD prophylaxis; history of aGVHD; and current cGVHD staging information.

Cancer history and underlying hematologic disease will also be summarized.

6.2. Disposition of Participants

The number and percentage of participants who were randomized, treated, completed treatment, discontinued study treatment with a primary reason for discontinuation, and withdrew from the study with a primary reason for withdrawal will be summarized for the safety run-in population and the Part 1 expansion population.

6.3. Protocol Deviations

Protocol deviations recorded on the eCRF will be summarized and presented in the participant data listings.

6.4. Exposure

For participants in the safety run-in population and participants in the Part 1 expansion, exposure to itacitinib and corticosteroids will be summarized descriptively as follows.

- **Duration of treatment with itacitinib:**

The exposure start date is when trt = itacitinib and exposure timepoint = first dose; when a participant does not have first dose record (but has other timepoints) as the exposure timepoint, exposure start date should be when trt = itacitinib and dose is not missing.

Duration of treatment (days) = Date of last dose of itacitinib – Date of first dose of itacitinib + 1.

- **Average daily dose of itacitinib:**

Average daily dose (mg/day) = Total actual itacitinib dose taken (mg) / Duration of treatment with itacitinib (days).

- **Dose modifications of itacitinib:**

Numbers of participants who had itacitinib dose reduction and/or interruption will be summarized. Separate summaries will be generated for participants with dose change due to dose tapering (change of dose due to efficacy of treatment) and participants with dose change due to other reasons (potential safety concerns).

- **Duration of treatment with corticosteroids:**

For corticosteroids, the first exposure start date is when the dose is not missing.

Duration of treatment (days) = Date of last dose of corticosteroid – Date of first dose of corticosteroid + 1.

If a participant is being treated with a corticosteroid prior to Day 1, study Day 1 will be used if no other data are available to conform to the definition provided in Section 4.1.1. If a participant is prescribed a corticosteroid for a flare during the course of the study, duration of treatment will be adjusted to account for the break in treatment between completing taper and starting of a short pulse for a flare.

- **Average daily dose of corticosteroids:**

Average daily dose (mg/day) = Total actual corticosteroid dose taken (mg) / Duration of treatment with corticosteroids (days).

Daily dose will account for how the doses are prescribed (eg, BID is converted to twice daily).

- **Reduction in daily dose of corticosteroids and successful tapering of corticosteroids**

Numbers of participants who had dose reduction and/or interruption of corticosteroids will be summarized as follows:

- Summary of number of participants with $\geq 50\%$ reduction in daily corticosteroid dose at Day 180
- Summary of participants successfully tapered off all corticosteroids at Day 180
- Summary of number of participants with $\geq 50\%$ reduction in daily corticosteroid dose by (4-week) time interval up to Month 6
- Summary of participants successfully tapered off all corticosteroids by (4-week) time interval up to Month 6

Participants will be considered as having a competing risk at the time of cGVHD progression or start of a new systemic therapy for cGVHD, relapse of the underlying hematologic disease, or death.

Sensitivity analyses may be performed for participants who had their corticosteroid dose increased during the corticosteroid taper period for a non-GVHD medical condition.

6.5. Study Drug Compliance

For participants in the safety run-in population and participants in the Part 1 expansion, overall compliance (%) for the study treatment will be calculated for all participants as follows:

$$\text{Compliance (\%)} = 100 \times [\text{total dose actually taken}] / [\text{total prescribed dose}].$$

The total prescribed dose is defined as the sum of the doses prescribed by the investigator accounting for dose modifications.

6.6. Prior and Concomitant Medication

For participants in the safety run-in population and participants in Part 1 expansion, prior medications and concomitant medications will be coded using the WHO Drug Dictionary and summarized by WHO drug class and WHO drug term. Results will be summarized as number and percentage of participants with prior and concomitant medications by PT and WHO drug class.

7. EFFICACY

[Appendix A](#) provides a list of planned tables, figures, and listings.

7.1. General Considerations

In Part 1, all efficacy analyses will be performed using the safety run-in population. In Part 1 Expansion, all efficacy analyses will be performed using the safety population.

If there are not sufficient data for meaningful statistical inference, the planned analysis will not be performed, and only related summary statistics and/or listings will be provided.

In all efficacy analyses, initiation of new systemic anti-GVHD therapy includes 4 scenarios:

1. Initiation of new anti-GVHD therapy including a higher dose of corticosteroid than that used at Day 1.
2. The need for a second dose increase in corticosteroids.
3. A dose increase in corticosteroids that is not tapered back to the previous dose of corticosteroids within 6 weeks (\pm 2 days) of the increase.
4. Reintroduction of systemic corticosteroids that occurs after complete taper of corticosteroids due to response.

No formal statistical tests will be performed.

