10.2. Populations for Analysis

The populations that will be included in study-related analyses are described in Table 24.

Table 24: Populations for Analysis

Population	Description			
ITT	All randomized participants.			
Safety	The safety population includes all enrolled/randomized participants who received at least 1 dose of study drug and/or reference therapy. Treatment groups for this population will be determined according to the actual treatment the participant received regardless of assigned study drug treatment.			
Safety run-in	All participants enrolled in the safety run-in portion of the study taking at least 1 dose of study drug and/or reference therapy comprise the safety run-in population. Treatment groups for this population will be determined according to the treatment assignment on Day 1 regardless of the actual study drug the participant might take during his/her continued participation in the study.			
PK evaluable	The PK evaluable population will include all participants who received at least 1 dose of study drug and/or reference therapy and provided at least 1 corresponding postdose plasma sample (1 PK measurement).			

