7.3. Analyses of the Secondary Efficacy Parameters

7.3.1. Response Rate

Response rate at 3, 6, and 12 months (Days 90, 180, and 365) is defined as the proportion of participants who achieved a response (CR or PR) at each of these timepoints based on an ITT population.

A participant will not be considered a responder for the analysis of ORR at 3, 6, and 12 months if any of the following events occurred at or prior to the response assessment at the predefined timepoint:

- cGVHD progression per NIH response criteria or initiation of a new systemic therapy for cGVHD

- Evidence of progression of the underlying hematologic disease
- Withdrawal from the study
- Death
- Response assessment missing (not performed) at the predefined timepoint

The proportion of responders will be estimated with 95% CIs. Confidence intervals will be calculated based on the exact method for binomial distributions. Summary statistics will be provided.

Additional analyses may be performed based on evaluable subsets. An evaluable population will also be considered with participants who have completed 3, 6, or 12 months of follow-up as of the cutoff date or discontinued earlier because of new cGVHD progression. Presentations of ORR at Month 3 and Month 6 will include a footnote explaining what "evaluable" means (ie, participants who had at least 3 or 6 months of follow-up as of the cutoff date or discontinued earlier).

Summary statistics and 95% CI will be provided by cohort. The primary comparisons in Part 1 expansion will involve only the 2 itacitinib groups (Treatment Groups A and B) and the corticosteroids-only group (Treatment Group D) as a result of Protocol Amendment 8, in which Treatment Group C (300 mg BID + corticosteroids) was discontinued. Data from Treatment Group C will be presented only as summary statistics and will not be subjected to any statistical comparison.

Pairwise Cochran-Mantel-Haenszel tests will be conducted for Month 6 response rate for each of the 2 itacitinib groups (Treatment Groups A and B) and the corticosteroids-only group (Treatment Group D) as an exploratory analysis.

The secondary endpoints discussed below will be summarized by Treatment Groups A, B, and D using the ITT population for efficacy-related endpoints and all groups for safety-related endpoints.

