11.1. Changes to Protocol-Defined Analyses

Note that the ITT population is equivalent to the safety analysis set as defined in the Protocol.

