APPENDIX A. PLANNED TABLES AND LISTINGS

This appendix provides a list of the planned tables, figures, and listings for the Clinical Study Report. Standard tables will follow the conventions in the Standard Safety Tables v1.4. In-text tables are identical in structure and content to appendix tables but follow a Rich Text Format.

Efficacy will use the safety analysis set as described in Section [5.3](#).

Tables

| Table No. | Title | Population |
|-----------|--|------------|
| 1.1.1.1 | Analysis Populations – Part 1 Expansion | Safety |
| 1.1.1.2 | Analysis Populations – Part 1 and Part 1 Expansion | Safety |
| 1.1.2.1 | Summary of Participant Disposition – Part 1 Expansion | Safety |
| 1.1.2.2 | Summary of Participant Disposition – Part 1 and Part 1 Expansion | Safety |
| 1.1.3.1 | Summary of Protocol Deviations – Part 1 Expansion | Safety |
| 1.1.3.2 | Summary of Protocol Deviations – Part 1 and Part 1 Expansion | Safety |
| 1.2.1.1 | Summary of Demographics – Part 1 Expansion | Safety |
| 1.2.1.2 | Summary of Demographics – Part 1 and Part 1 Expansion | Safety |
| 1.3.1.1.1 | Summary of Baseline Disease Characteristics for Cancer History – Part 1 Expansion | Safety |
| 1.3.1.1.2 | Summary of Baseline Disease Characteristics for Cancer History – Part 1 and Part 1 Expansion | Safety |
| 1.3.1.2.1 | Summary of Baseline Disease Characteristics for GVHD – Part 1 Expansion | Safety |
| 1.3.1.2.2 | Summary of Baseline Disease Characteristics for GVHD – Part 1 and Part 1 Expansion | Safety |
| 1.3.2.1 | Summary of Allogeneic Hematopoietic Stem Cell Transplant History – Part 1 Expansion | Safety |
| 1.3.2.2 | Summary of Allogeneic Hematopoietic Stem Cell Transplant History – Part 1 and Part 1 Expansion | Safety |
| 1.3.2.3 | Summary of Karnofsky Scale | Safety |
| 1.3.3.1 | Summary of Prior Anticancer Therapy – Part 1 Expansion | Safety |
| 1.3.3.2 | Summary of Prior Anticancer Therapy – Part 1 and Part 1 Expansion | Safety |
| 1.4.1.1 | Summary of Prior Medications – Part 1 Expansion | Safety |
| 1.4.1.2 | Summary of Prior Medications – Part 1 and Part 1 Expansion | Safety |
| 1.4.2.1 | Summary of Concomitant Medications – Part 1 Expansion | Safety |
| 1.4.2.2 | Summary of Concomitant Medications – Part 1 and Part 1 Expansion | Safety |
| 1.5.1.1 | Summary of General Medical History – Part 1 and Part 1 Expansion | Safety |
| 1.5.1.2 | Summary of Conditioning and Prophylaxis Therapy – Part 1 and Part 1 Expansion | Safety |

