| 2.2.1 | Summary of Overall Response Rate at Months 3, 6, and 12 | Safety |
| 2.2.2 | Summary of Nonrelapse Mortality Rate | Safety |
| 2.2.3 | Summary of Duration of Response | Safety |
| 2.2.4 | Summary of Time to Response | Safety |
| 2.2.5 | Summary of Relapse Rate of Malignant and Nonmalignant Hematologic Diseases | Safety |
| 2.2.6 | Summary of Time to Primary Hematologic Disease Relapse | Safety |
| 2.2.7 | Summary of Overall Survival | Safety |
| 2.2.8 | Summary of Best Overall Response | Safety |
| 2.2.8.1 | Summary of Best Overall Response by GVHD Organ Involved | Safety |

| Table No. | Title | Population |
|-----------|---|------------|
| 2.2.8.2 | Summary of Best Overall Response for Skin Sclerotic Findings Subgroup | Safety |
| 2.2.9 | Summary of Failure-Free Survival | Safety |
| 2.2.11 | Summary of Number of Participants With $\geq 50\%$ Reduction in Daily Corticosteroid Dose at Day 180 | Safety |
| 2.2.12 | Summary of Participants Successfully Tapered Off All Corticosteroids at Day 180 | Safety |
| 2.2.13 | Summary of Number of Participants With $\geq 50\%$ Reduction in Daily Corticosteroid Dose by (4-Week) Time Interval Up to Month 6 | Safety |
| 2.2.14 | Summary of Participants Successfully Tapered Off All Corticosteroids by (4-Week) Time Interval Up to Month 6 | Safety |
| 3.1.1 | Summary of Itacitinib Exposure, Duration of Exposure, and Dose Adjustment | Safety |
| 3.1.2 | Summary of Itacitinib Compliance | Safety |
| 3.1.3 | Summary of Corticosteroid Exposure, Duration of Exposure, and Dose Adjustment | Safety |
| 3.2.1 | Overall Summary of Treatment-Emergent Adverse Events | Safety |
| 3.2.2 | Summary of Treatment-Emergent Adverse Events by MedDRA System Organ Class and Preferred Term | Safety |
| 3.2.3 | Summary of Treatment-Emergent Adverse Events by MedDRA Preferred Term in Decreasing Order of Frequency | Safety |
| 3.2.4 | Summary of Treatment-Emergent Adverse Events by MedDRA System Organ Class, Preferred Term, and Maximum Severity | Safety |
| 3.2.5 | Summary of Itacitinib Treatment-Related, Treatment-Emergent Adverse Events by MedDRA System Organ Class and Preferred Term | Safety |
| 3.2.6 | Summary of Itacitinib Treatment-Related, Treatment-Emergent Adverse Events by MedDRA Preferred Term in Decreasing Order of Frequency | Safety |
| 3.2.7 | Summary of Itacitinib Treatment-Related, Grade 3 or Higher Treatment-Emergent Adverse Events by MedDRA System Organ Class, and Preferred Term | Safety |

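### The SAP assigns Part 1 expansion efficacy to the as-treated safety set in one place and to ITT in another, and joins them with an equivalence statement that its own definitions contradict

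*SAP*

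**What the plan says.** The SAP gives two instructions for the same tables.

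- **Safety set.** SAP 7.1: "In Part 1 Expansion, all efficacy analyses will be performed using the safety population". The Appendix A preamble repeats this: "Efficacy will use the safety analysis set as described in Section" (it points to 5.3). The table list agrees, with Table 2.2.1 reading "Summary of Overall Response Rate at Months 3, 6, and 12 | Safety". Every other efficacy table through 2.2.14 has the same label.
- **ITT.** SAP 7.3.1 defines the response rate as the proportion who "achieved a response (CR or PR) at each of these timepoints based on an ITT population". It then adds: "The secondary endpoints discussed below will be summarized by Treatment Groups A, B, and D using the ITT population for efficacy-related endpoints". Protocol 10.4.2.2 also names ITT for its listed secondary efficacy endpoints. Its paragraph on Month 3 and Month 6 response names no population.
- **Bridge.** SAP 11.1: "Note that the ITT population is equivalent to the safety analysis set as defined in the Protocol".
- **Definitions.** In Protocol Table 24 and SAP Table 4, ITT is everyone randomized, with no dosing condition. For the safety set, Protocol 10.2 says: "The safety population includes all enrolled/randomized participants who received at least 1 dose of study drug and/or reference therapy". SAP 5.3 adds the grouping rule: "Treatment groups for this population will be determined according to the actual treatment the participant received regardless of assigned study drug treatment".

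**The concern.** The two sets differ in who is counted and in which arm they are counted. Someone randomized who takes nothing is in ITT but not in the safety set. Someone randomized to Group A or B who takes only corticosteroids stays in the safety set, because reference therapy is enough for membership. Grouped by actual treatment, that person may be tabulated with Group D; no passage says how the case is handled.

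Two programmers could therefore produce different Month 6 tables, and the safety-set version does not preserve the comparison by randomized assignment. The direction of the bias is not fixed:

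- It favours itacitinib if non-starters in those arms are nonresponders. Those who withdraw are nonresponders under SAP 7.3.1.
- It goes against itacitinib if regrouped participants respond on corticosteroids alone, or if the non-starters come from Group D.

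Month 3 and Month 6 response are the key secondary endpoints of the expansion. They support dose selection (Protocol 6.1.1.4, SAP 7.2), and Month 6 response feeds the pairwise CMH tests against Group D (SAP 7.3.1) and the posterior probability in SAP 3.3.2.

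**Working it through.** **Step 1: are the sets equivalent by definition?**

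| | ITT | Safety |
|---|---|---|
| Membership | Randomized | At least one dose of itacitinib or corticosteroid |
| Grouping | No as-treated rule | Treatment actually received |

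They coincide only if every randomized participant was dosed and received the assigned treatment. The SAP does not state that condition. Divergence is possible: Protocol 8.1.2 allows up to 2 days between randomization and first dose, and the expansion is open-label. Protocol 2.3.2 reports a participant in an earlier itacitinib study who was randomized and withdrew before treatment.

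**Step 2: reproduce the plan's posterior table.** Protocol Table 23 (SAP Table 3) gives the posterior probability of a clinically meaningful Month 6 difference at 35 per group. The prior and margin cannot be read in the public text, so they are inferred. With s responders out of n and a Beta(1,1) prior, each posterior is Beta(1+s, 1+n−s), and

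P(p_T − p_C > d) = ∫ f_C(p) · [1 − F_T(p + d)] dp

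where f_C is the Group D posterior density and F_T the itacitinib posterior distribution function. With d = 0.15 this reproduces all 30 cells to within 0.05 percentage points. A Beta(0.5,0.5) prior with the same margin misses by up to 1.8 points. Margins of 0.10, 0.12 and 0.20 with the Beta(1,1) prior miss by up to 18.6, 11.3 and 19.3 points.

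**Step 3: change one participant.** The starting point is 26/35 (itacitinib) against 20/35 (Group D). The number of affected participants is an assumption.

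| Handling | Itacitinib | Group D | Difference (points) | Posterior | Shift over all 30 cells (points) |
|---|---|---|---|---|---|
| ITT | 26/35 | 20/35 | 17.1 | 54.9% | reference |
| Itacitinib nonresponder dropped | 26/34 | 20/35 | 19.3 | 62.2% | +1.9 to +8.3 |
| Itacitinib nonresponder moved to D | 26/34 | 20/36 | 20.9 | 67.4% | +2.6 to +14.3 |
| Itacitinib responder moved to D | 25/34 | 21/36 | 15.2 | 47.9% | −1.8 to −7.3 |
| Group D nonresponder dropped | 26/35 | 20/34 | 15.5 | 49.0% | −1.5 to −6.7 |
| One nonresponder dropped from each arm | 26/34 | 20/34 | 17.6 | 56.5% | +0.6 to +2.2 |

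Example for the second row: 26/34 = 76.5% and 20/35 = 57.1%, a difference of 19.3 points before rounding.

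**The case against.** The best reply is that the operative instruction is clear. SAP 7.1, the Appendix A preamble and every efficacy table label say safety set. SAP 11.1 maps ITT onto it under a heading about changes to Protocol-defined analyses, so it may have been meant as a declared switch. If so, it is worded as an equivalence, gives no reason, and leaves SAP 7.3.1 on ITT.

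Several limits do stand:

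- The sentence is false as a matter of definition; the sets could still coincide in the data.
- A participant is dropped only by taking neither itacitinib nor any corticosteroid. That should be uncommon in active moderate or severe disease with treatment starting within 2 days. The regrouping scenarios need an itacitinib-arm participant who never takes itacitinib.
- The figures cover Month 6 response only, where the Protocol paragraph is silent on population (SAP 7.3.1 is not). Duration of response and time to response are summarized among responders, so dropping a non-starter who never responded changes neither summary.
- There is no formal test, the CMH tests are exploratory, and dose selection is primarily on adverse events. No decision threshold is visible, so no shift can be shown to change a decision.

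Two further points do not defeat the change. SAP 6.4 lists the corticosteroid-reduction summaries under exposure, but Protocol 10.4.2.2 and SAP 7.3.9 treat the Day 180 versions as efficacy. Whether Part 1 participants are pooled into Group A also affects the randomized comparison, but that is a separate question which naming ITT does not settle.

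**Conclusion.** The concern holds. The SAP contradicts itself on the efficacy population, its safety-set rule departs from the ITT specification in Protocol 10.4.2.2 for the listed endpoints, and the equivalence statement fails against both documents' definitions. Followed literally, SAP 7.1 would drop or regroup randomized participants.

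The consequence is moderate. Type I error is not at stake. In the scenarios examined, one participant moves the Month 6 posterior by between −7.3 and +14.3 points across the 30 tabulated cells. These figures rest on the inferred Beta(1,1) priors and 15-point margin, and on an assumed count of one affected participant (one per arm in the last scenario). With no such participants the effect is zero. The point should be fixed because the plan should fix one denominator without relying on how the data turn out.

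**What to change.** 1. In SAP 7.1 and Appendix A, set the population for Part 1 expansion efficacy tables 2.2.1 to 2.2.14 to ITT: all randomized, by assigned group. State explicitly that this includes Month 3 and Month 6 response.
2. Delete the equivalence sentence in SAP 11.1.
3. Keep the as-treated safety set for safety and exposure tables and, if wanted, for a labelled sensitivity analysis of Month 6 response.
4. Say how an undosed participant counts in the Day 180 corticosteroid endpoints, because SAP 4.1.1 and 7.3.9 define Day 1 and the starting dose from dosing.

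The cost is SAP wording and a population flag in the efficacy programs, with no new data. Response rates may move slightly in either direction, or not at all if the sets coincide.
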